2.4.2. Safety Analysis Set

Safety analyses for both Part 1 and Part 2 will be performed on the safety analysis set, which is defined as all treated subjects who received at least 1 injection of study agent (partial or complete). For the safety analyses in Part 1, subjects will be analyzed according to the actual treatment received during the study irrespective of the treatment assigned at randomization.

Safety analyses for LTE will be performed on the safety analysis set including all subjects who entered into LTE and received at least 1 injection at or after Week 52.

2.4.3. Pharmacokinetics Analysis Set

The PK analysis set is defined as subjects who received at least one injection of guselkumab and have at least one valid blood sample drawn for PK analysis.

2.4.4. Immunogenicity Analysis Set

The immunogenicity analysis set is defined as all subjects who received at least one injection of guselkumab and have appropriate samples for the detection of antibodies to guselkumab.

In both PK and immunogenicity analyses, subjects will be analyzed according to the actual treatment received.

2.5. Definition of Subgroups

To evaluate the consistency of efficacy based on demographic characteristics, baseline disease characteristics, and psoriasis medication history, subgroup analyses will be performed for the co-primary endpoints. The subgroups include, but are not limited to, the following:

Baseline demographics:

- Sex (male, female)
- Race
- Region (North America/Australia/Brazil, Europe)
- Baseline Age (≥ 6 to <12 years, ≥ 12 to <18 years)
- Baseline weight (<70 kg, ≥ 70 kg)

Baseline disease characteristics:

- Age at diagnosis (years) (< 8 , ≥ 8)
- Psoriasis disease duration (years) (< 3 , ≥ 3)
- Baseline PASI (<20 , ≥ 20)
- Baseline IGA (<4 , $=4$)
- Baseline BSA ($<20\%$, $\geq 20\%$)
- Psoriatic arthritis (Yes, No)
- Baseline CDLQI (< 10 , ≥ 10)

Psoriasis medication history:

- Phototherapy (ultraviolet B light [UVB] or psoralen and ultraviolet A light therapy [PUVA])
 - Never used
 - Ever used
- Non-biologic systemics (PUVA, MTX, cyclosporine, acitretin, apremilast, or tofacitinib)
 - Never used
 - Ever Used

- Biologics (infliximab, alefacept, efalizumab, ustekinumab, briakinumab, secukinumab, ixekizumab, brodalumab, or adalimumab)
 - Never used
 - Ever Used
- Non-biologic systemics or biologics (as defined above)
 - Never used
 - Ever used

2.6. Study Day

Study Day 1 refers to the first study agent administration date. The study day for an event is defined as:

- Event date - (date of Study Day 1) +1, if event date is \geq date of Day 1
- Event date - date of Day 1, if event date $<$ date of Day 1

2.7. Baseline

In general, the baseline measurement is defined as the closest measurement taken prior to or on the day of the first study agent administration unless otherwise specified.

3. INTERIM ANALYSIS AND DATA MONITORING COMMITTEE REVIEW

3.1. Interim Analysis

One interim analysis is planned for this study after all participants ≥ 12 to < 18 years of age in Part 1a have completed Week 16. All available guselkumab PK data for participants ≥ 12 to < 18 years of age through Week 16 will be evaluated via modeling and simulation, to determine if the body weight-based dose used in Part 1a provided exposure comparable to adults, or whether a revised body weight-based dose should be instituted in Part 1b. This evaluation will be conducted by sponsor personnel who are otherwise not participating in the conduct of this study. Efficacy data will not be analyzed in the interim analyses and no adjustment will be made for the significance level.

Details of the interim analyses are included in a separate interim analysis plan.

3.2. Data Monitoring Committee

The DMC will be an independent committee of 3 members and will include individuals with expertise in pediatric dermatology, and biostatistics. None of the members will be participating as investigators in the study. The major function of this committee will be to monitor the safety of the study intervention. The DMC will periodically review tabulated safety summaries and any additional safety data that the DMC may request during the conduct of the study. Prior to any DMC review, the DMC charter will define and document the content of the safety summaries, the DMC's role and responsibilities, and the general procedures (including communications).

Prior to enrollment of participants ≥ 6 to < 12 years of age in Part 1b and enrollment of participants ≥ 12 to < 18 years of age into Part 2, the DMC will review all available safety data once all participants enrolled in Part 1a of the study have completed their Week 16 visit or discontinued from the study, and provide a recommendation as to whether the sponsor can initiate enrollment of Part 1b and Part 2. Additionally, prior to enrollment of participants ≥ 6 to < 12 years of age into Part 2, the DMC will review all available safety data once all participants in Part 1b have completed 16 weeks of treatment or discontinued from the study, and provide a recommendation as to whether enrollment of participants ≥ 6 to < 12 years of age into Part 2 can be initiated.

Details of the DMC safety reviews are included in a separate DMC Charter and DMC SAP. The DMC SAP contains definitions of analysis sets, derived variables, scope and objects of the DMC, data-cutoff points, statistical methods and output to be produced for the safety reviews as required by the DMC Charter. Additionally, a dedicated DMC Data Presentation Specifications (DPS) document details output and programming specifications.

4. SUBJECT INFORMATION

Unless otherwise noted, the subject information analyses will be performed based on the full analysis sets for Part 1 and Part 2 of the study. The number of subjects in each part of the study and in each analysis set will be summarized by assigned treatment group and overall. In addition, the distribution of subjects by region, country, and site will be presented.

Simple descriptive statistics, such as mean, median, standard deviation, interquartile range, maximum, and minimum for continuous variables, and counts and percentages for discrete variables will be used to summarize most data and no formal statistical analyses for comparisons of subject information between treatment groups will be performed. In addition, subject listings will also be used to present the data.

4.1. Demographics and Baseline Characteristics

4.1.1. Demographics

Table 3 presents a list of the demographic variables that will be summarized by treatment group, and overall for the full analysis set in Part 1 and Part 2 of the study.

Age will be calculated as $(\text{date of informed consent} - \text{date of birth} + 1) / 365.25$ in units of years.

BMI will be calculated as $\text{weight}/\text{height}^2$ with units of kg/m^2 .

Table 3: Demographic Variables	
Continuous Variables:	Summary Type
Age (years)	Descriptive statistics (N, mean, standard deviation [SD], median and range [minimum and maximum], and IQ range).
Weight (kg)	
Height (cm)	
BMI (kg/m^2)	
Categorical Variables:	

Age (≥ 6 to <12 years, ≥ 12 to <18 years)	Frequency distribution with the number and percentage of subjects in each category.
Weight (<70 kg, ≥ 70 kg)	
Sex (male, female)	
Race ^a (American Indian or Alaska Native, Asian, Black or African American, Native Hawaiian or other Pacific Islander, White, Other, Multiple)	
Ethnicity (Hispanic or Latino, not Hispanic or Latino)	

^aIf multiple race categories are indicated, then Race is recorded as “Multiple.”

In addition, the histogram plots for the distributions of age at baseline will be provided.

4.1.2. Baseline Characteristics

Psoriasis baseline disease characteristics (i.e., psoriasis disease duration [years], age at diagnosis [years], BSA [%], psoriatic arthritis, baseline IGA score, baseline PASI score [0-72], baseline FDLQI, and baseline CDLQI) will be summarized by treatment group for Part 1 and Part 2.

4.2. Disposition Information

Disposition information will be based upon the full analysis set. The number of subjects in the following disposition categories will be summarized for the periods through Week 16 and through Week 52 for Part 1, for the period through Week 52 for Part 2, and for the period of the LTE:

- Subjects randomized (Part 1 only)
- Subjects treated
- Subjects who completed the study
- Subjects who discontinued study agent and reasons for discontinuation
- Subjects who terminated study prematurely and reasons for termination

Listings of subjects will be provided for the following categories:

- Subjects who discontinued study agent
- Subjects who terminated study prematurely
- Subjects who were unblinded during the study period (Part 1 only)
- Subjects who were randomized but did not receive study agent (Part 1 only) and subjects who enrolled but did not receive study agent (Part 2 only)
- Subjects who met treatment failure criteria and reason
- Subjects who used rescue medication (Part 1 only)

4.3. Treatment Compliance

For Part 1, study agent compliance will be summarized descriptively for the full analysis set. The number of subjects by randomized treatment versus actual treatment will be presented in a summary table.

Additionally, the study agent lots received by treatment, including matching placebo for active treatment will be summarized.

4.4. Extent of Exposure

The exposure data will be summarized through Week 16, through Week 52, and through LTE. The number of active study agent injections, and the cumulative dose of study agent will be summarized by treatment group for the safety analysis set.

In addition, the number of subjects who were withdrawn and retreated with guselkumab after Week 16, and the number of subjects who initiated guselkumab after Week 16 will be summarized for Part 1.

4.5. Protocol Deviations

In general, the following list of major protocol deviations may have the potential to impact subjects' rights, safety or well-being, or the integrity and/or results of the clinical trial. Subjects with major protocol deviations will be identified prior to database lock and the subjects with major protocol deviations will be summarized by category.

- Entered but did not satisfy criteria
- Developed withdrawal criteria but not withdrawn
- Received a disallowed concomitant treatment
- Received a wrong treatment or an incorrect dose
- Other

The above summaries will be presented through Week 16 and through Week 52 for Part 1 by randomized treatment group, through Week 52 for Part 2 of the study, and through the end of study for subjects who continued in the LTE period. Subjects with major protocol deviations will also be listed.

4.6. Prior and Concomitant Medications

Subjects' prior psoriasis medication history with topical agents, phototherapy, non-biologic systemic therapies, and biologic medications will be summarized by treatment group for the full analysis set for Part 1 and Part 2 of the study. See Section for lists of medications in each category. In addition, reasons for which subjects discontinued previous systemic therapies (contraindication, inadequate response, intolerance [ie, AEs], or other) will be summarized by treatment group.

The number of subjects who received concomitant treatment with a moisturizer for psoriasis will also be summarized through Week 16 for Part 1.

Subjects who received the following concomitant medications will be listed:

- Corticosteroids (intralesional, IV or oral) for indications other than psoriasis and/or psoriatic arthritis
- Intra-articular corticosteroids

5. EFFICACY

Unless otherwise stated, efficacy data summaries will be provided for the full analysis set for each part. The Fisher's exact test, stratified by age group and region, will be used to compare the proportion of subjects responding to treatment if appropriate. Continuous response parameters (i.e. change from baseline in CDLQI) will be compared using Mixed Model Repeat Measurement (MMRM) analysis with factors of treatment, region, age group, baseline, visit, baseline by visit and treatment by visit; or an analysis of covariance (ANCOVA) model, adjusting for baseline value, age group, and region. If the normality assumption is violated, non-parametric methods will be used as appropriate. All statistical testing will be performed at a 2-sided significance level of 0.05.

Descriptive statistics, such as mean, median, standard deviation, minimum and maximum, interquartile range for continuous variables, and counts and percentages for categorical variables will be used to summarize the data. Life table estimates will be provided for the time to event variables. Graphical data displays and subject listings may also be used to summarize the data.

5.1. Analysis Specifications

5.1.1. Level of Significance

All statistical procedures to test superiority hypotheses will be performed at a 2-sided significance level of 0.05. This study is designed to maintain an overall Type I error of 0.05 or less for the co-primary analyses and major secondary analyses. Nominal p-values will be reported for other secondary analyses.

5.1.1.1. Multiplicity Adjustment for Testing Procedures

US-FDA specific primary and major secondary endpoints and analyses are defined in Section 5.4. Globally (i.e., regions other than the United States), the following primary and major secondary endpoints will be tested. There are 2 co-primary endpoints in this study:

- The proportion of subjects who achieve an IGA score of cleared (0) or minimal (1) at Week 16
- The proportion of subjects who achieve a PASI 75 response at Week 16

Both of the co-primary endpoint analyses will be compared between the guselkumab treatment group and the placebo group and tested at a 2-sided α -level of 0.05. If one of the comparisons is not significant at the 2-sided α -level of 0.05, the co-primary endpoints will be considered not significant.

In addition, there are 4 major secondary endpoints in this study to be compared between the guselkumab group and the placebo group:

- The proportion of subjects who achieve a PASI 90 response at Week 16.
- The proportion of subjects who achieve an IGA score of cleared (0) at Week 16.
- The proportion of subjects who achieve a PASI 100 response at Week 16.
- The change from baseline in CDLQI at Week 16

In order to control the overall Type 1 error rate, the co-primary analyses and major secondary analyses will be tested in a fixed sequence as ordered above. That is, the analyses of the major secondary endpoints will be performed only if both primary analyses are significant, and will be performed in the fixed sequence testing approach, as specified above. If a given comparison between the guselkumab treatment group and the placebo group is not significant at the 2-sided α -level of 0.05, the remaining treatment group comparisons in this sequence will be considered not significant and will be considered as supportive analyses.

5.1.2. Definition of the Efficacy Endpoints and Calculation of the Efficacy Instruments

5.1.2.1. Investigator's Global Assessment

The Investigator's Global Assessment (IGA) documents the investigator's assessment of the subject's psoriasis at a given time point. Overall lesions are graded for induration, erythema, and scaling. The patient's psoriasis is assessed as cleared (0), minimal (1), mild (2), moderate (3), or severe (4).

Efficacy endpoints related to the IGA score are defined below:

IGA cleared responder

Subjects who achieve an IGA score of cleared (0) will be considered IGA cleared responders.

IGA cleared or minimal responder

Subjects who achieve an IGA score of cleared (0) or minimal (1) will be considered IGA cleared or minimal responders.

IGA mild or better responder

Subjects who achieve an IGA score of cleared (0), minimal (1), or mild (2) will be considered IGA mild or better responders.

5.1.2.2. Psoriasis Area and Severity Index

The PASI is a system used for assessing and grading the severity of psoriatic lesions and their response to therapy. In the PASI system, the body is divided into 4 regions: the head, trunk, upper extremities, and lower extremities. Each of these areas is assessed separately for the percentage of the area involved, which translates to a numeric score that ranges from 0 (indicates no involvement) to 6 (90%-100% involvement), and for erythema, induration, and scaling, which are each rated on a scale of 0 to 4. The PASI produces a numeric score that can range from 0 (no psoriasis) to 72. A higher score indicates more severe disease.

Efficacy endpoints related to the PASI score are defined below:

PASI 50 Responder

Subjects with $\geq 50\%$ improvement in PASI from baseline will be considered PASI 50 responders.

PASI 75 Responder

Subjects with $\geq 75\%$ improvement in PASI from baseline will be considered PASI 75 responders.

PASI 90 Responder

Subjects with $\geq 90\%$ improvement in PASI from baseline will be considered PASI 90 responders.

PASI 100 Responder

Subjects with 100% improvement in PASI from baseline (PASI score=0) will be considered PASI 100 responders.

Loss of PASI 90 Response

Defined as $< 90\%$ improvement in PASI from baseline after Week 16 in a participant who had achieved $\geq 90\%$ improvement in PASI from baseline at Week 16.

Loss of 50% of PASI Improvement

Defined as a loss of $\geq 50\%$ of the improvement in PASI at Week 16 after treatment is withdrawn.

5.1.2.3. Body Surface Area

The percentage of a participant's total body surface area affected by psoriasis will be assessed.

5.1.2.4. Children Dermatology Life Quality Index

The Children Dermatology Life Quality Index (CDLQI) is a dermatology-specific quality of life instrument designed to assess the impact of the disease on a subject's quality of life. It is an adapted version of DLQI. The CDLQI, a 10-item questionnaire has a 4 item response option and a recall period of 1 week. The instrument is designed for use in children (ie, participants from 4 to 16 years of age), is self-explanatory and can be simply handed to the participant who is asked to fill it in with the help of the child's parent or caregiver. In addition to evaluating overall quality of life, the CDLQI can be used to assess 6 different aspects that may affect quality of life: symptoms and feelings, leisure, school or holidays, personal relationships, sleep, and treatment. The scoring of each question is as follows:

Very much	Scored 3
Quite a lot	Scored 2
Only a little	Scored 1
Not at all	Scored 0
Question unanswered	Scored 0
Question 7: Prevented school	Scored 3

The CDLQI is calculated by summing the score of each question resulting in a maximum of 30 and a minimum of 0. A higher score indicates more severe disease. The 6 CDLQI components scores are calculated as follows:

Symptoms and feelings	Questions 1 and 2	Score maximum 6
Leisure	Questions 4, 5 and 6	Score maximum 9
School or holidays	Questions 7	Score maximum 3
Personal relationships	Questions 3 and 8	Score maximum 6
Sleep	Questions 9	Score maximum 3
Treatment	Questions 10	Score maximum 3

5.1.2.5. Family Dermatology Life Quality Index

The FDLQI is a dermatology-specific quality of life instrument for the family members of patients having any skin disease. It has 10 items asking the family members/partners about the impact of a patient's skin disease on different aspects of their quality of life (e.g. emotional, physical well-being, relationships, social life, leisure activities, burden of care, job/study, housework and expenditure). The frame of reference for items is over the last 1 month. Each item has a four-point response option, where Not at all/Not relevant = 0; A little = 1; Quite a lot = 2; and Very much = 3. The scores of individual items (0–3) are added to give a total scale score that ranges from 0 to 30; a higher score indicates greater impairment of quality of life. The FDLQI is designed to be used as an additional outcome measure in conjunction with the CDLQI or any other patient-completed questionnaire. This instrument should be completed by a participant's primary caregiver.

5.1.3. Data Handling Rules

The following treatment failure rules and data handling rules will be applied to the PASI, IGA, CDLQI, and FDLQI related efficacy analyses in this study.

5.1.3.1. Partial Component Score

PASI and IGA

For missing component scores in IGA and PASI data, the IGA and PASI total score will not be calculated and the value is missing. The data handling rules described in Section 5.1.3.3, 5.1.3.5, and 5.1.3.6 would apply.

CDLQI

For a partially answered questionnaire (eg, not all 10 answers in the CDLQI questionnaire were available) or incorrectly completed questionnaire in CDLQI, the following data handling rules would apply before applying the treatment failure rules and early escape rules:

- If one question is left unanswered, this question will be scored 0. The total score and each of the 6 component scores will then be calculated.
- If two or more questions are left unanswered, the total score and the affected component scores will be set to missing.

If both parts of question 7 are completed, the higher of the two scores should be used.

FDLQI

For a partially answered questionnaire in FDLQI, the following data handling rules would apply before applying the treatment failure rules and early escape rules:

- If one question is left unanswered, this is scored 0 and the scores are summed and expressed as usual out of a maximum of 30.
- If two or more questions are left unanswered the questionnaire is not scored.
- If two or more response options are ticked, the response option with the highest score should be recorded.
- If there is a response between two tick boxes, the lower of the two score options should be recorded.

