5.5.2.1.3. Analyses Related to CDLQI, FDLQI, and BSA

5.5.2.1.3.1. Through Week 16

- The proportion of subjects achieving a CDLQI of 0 or 1 will be summarized at Week 8 and Week 16 among randomized participants with a baseline CDLQI > 1. The proportion of subjects with CDLQI of 0 or 1 at Week 16 will be compared between the guselkumab group and the placebo group using Fisher's exact test stratified by pooled region and age group.
- The change from baseline in CDLQI total score will be summarized at Week 8 and Week 16.

- The change from baseline in each CDLQI component score will be summarized at Week 16.
- The proportion of subjects achieving a FDLQI of 0 or 1 will be summarized at Week 8 and Week 16 among randomized subjects with a baseline FDLQI > 1. The proportion of subjects with FDLQI of 0 or 1 at Week 16 will be compared between the guselkumab group and the placebo group using Fisher's exact test stratified by region and age group.
- The change from baseline in FDLQI total score will be summarized at Week 8 and Week 16. The change from baseline in FDLQI at Week 16 will be compared between the guselkumab group and the placebo group using a Mixed Model for Repeated Measures (MMRM) model to test the difference between treatment groups and adjust for missing data.
- The change from baseline in each FDLQI component score will be summarized at Week 16.
- The change from baseline in BSA at Week 16 will be compared between the guselkumab group and the placebo group using a MMRM model.
- BSA involved and change from baseline in BSA will be summarized over time through Week 16.

In addition, relevant comparisons for secondary analyses at Week 16 will also be conducted between the etanercept group and the placebo group.

5.5.2.1.3.2. From Week 16 through Week 52

PASI 90 responders at Week 16 (after withdrawal of guselkumab)

- CDLQI score will be summarized at Week 16 and Week 28 for subjects randomized to the guselkumab group who were PASI 90 responder at Week 16, and were withdrawn from study agent at Week 16. Subjects who were retreated with guselkumab prior to Week 28 will be excluded.
- FDLQI score will be summarized at Week 16 and Week 28 for subjects randomized to the guselkumab group who were PASI 90 responder at Week 16, and were withdrawn from study agent at Week 16. Subjects who were retreated with guselkumab prior to Week 28 will be excluded.

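### When question 7, 9 or 10 is the only CDLQI blank, its one-question component is scored 0, the best value, with no answer behind it

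*SAP*

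**What the plan says.** SAP 5.1.2.4 builds the CDLQI total (0 to 30) from ten questions and splits it into six components, introduced by "The 6 CDLQI components scores are calculated as follows". Three components rest on one question each: "School or holidays Questions 7 Score maximum 3", "Sleep Questions 9 Score maximum 3" and "Treatment Questions 10 Score maximum 3". The item table in that section gives a score of 0 both to the answer meaning no impact and to a question left blank, and sets no limit on the number of blanks.

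SAP 5.1.3.1 then handles incomplete forms by the number of blanks:

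- One blank: "If one question is left unanswered, this question will be scored 0", followed by "The total score and each of the 6 component scores will then be calculated".
- Two or more blanks: "If two or more questions are left unanswered, the total score and the affected component scores will be set to missing".

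For question 7, which has two parts, the higher score is used when both are completed. The question is therefore unanswered only when neither part is filled in. Neither section makes an exception for the one-question components.

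The component scores are used in two places in SAP 5.5.2.1.3. Through Week 16: "The change from baseline in each CDLQI component score will be summarized at Week 16". From Week 16 through Week 52, a matching Week 52 summary is listed under the Week 16 PASI 90 non-responders.

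**The concern.** Scoring one blank as 0 can be defended for a ten-question total, because the answered nine still carry the score. It does not carry over to a component that has only one question. There the imputed 0 is the whole score, and it equals the best answer a child could give.

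The treatment of the same blank also depends on an unrelated question. An unanswered question 9 gives Sleep = 0 if the rest of the form is complete, but Sleep = missing if question 4, a Leisure item, is blank too. Nothing is known about sleep in either case.

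At stake is the accuracy of the tables that show which aspects of a child's life changed.

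**Working it through.** **Inputs.** The question-to-component map and item scores come from SAP 5.1.2.4, the blank rules from SAP 5.1.3.1, and the planned Part 1 group sizes (guselkumab 40, placebo 25) from SAP 1.4.

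**Check of the plan's own figure.** The component maxima sum to 6 + 9 + 3 + 6 + 3 + 3 = 30, each question being used once. This matches the stated total maximum.

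**The rules applied to one form.** Assume, for illustration, that every true answer is 2, so the complete form totals 20.

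| Blank | Component(s) affected | Total |
|---|---|---|
| none | none (School, Sleep and Treatment are 2 each) | 20 |
| Q7 only (neither part) | School/holidays = 0 | 18 |
| Q9 only | Sleep = 0 | 18 |
| Q10 only | Treatment = 0 | 18 |
| Q1 only | Symptoms = 2 instead of 4 | 18 |
| Q1 and Q9 | Symptoms and Sleep missing | missing |

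The Q1 row shows the difference from a multi-question component, which still contains an answered item. For a one-question component the understatement is 0 to 3 points, up to 3/3 = 100% of its range. The same blank shifts the total by at most 3/30 = 10% of its range.

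**Direction in the change from baseline.** Take Sleep with a true baseline of 2.

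- Follow-up blank, true follow-up 2: recorded change 0 − 2 = −2, true change 0. Improvement is overstated.
- Baseline blank, true follow-up 0: recorded change 0 − 0 = 0, true change −2. Improvement is hidden.
- Baseline blank, true follow-up 1: recorded change 1 − 0 = +1, true change −1. A worsening appears that did not happen.
- If the true answer to the blank question was 0, the recorded value is right.

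**Effect on a Week 16 mean.** One form can shift a group mean by at most 3/n:

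- guselkumab: 3/40 = 0.075
- placebo: 3/25 = 0.12

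Both assume that the whole planned group contributes a value. They compare the recorded mean with the mean under the true answer. They are not the change the fix would produce, because the fix drops the form's value and does not recover the answer. With m the mean of the other children and d the recorded change, the reported mean would move by (m − d)/n, and neither m nor d is known.

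**Week 52.** These denominators do not apply there, because the summary covers only Week 16 PASI 90 non-responders. As an assumption, apply the adult PASI 90 rates of 70.0% and 73.3% (Protocol 2.2.1) to the 40 planned guselkumab children. That leaves 40 × 0.300 = 12 to 40 × 0.267 = 10.7, about 11, and a bound of 3/12 = 0.25 to 3/11 = 0.27 per form. Pediatric rates may differ.

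**What cannot be computed.** The documents give no frequency of single blanks, so no expected bias can be stated.

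**The case against.** The strongest reply is that this is ordinary scoring with little riding on it. The SAP's item table scores a blank as 0, and 5.1.3.1 limits that to one blank per form. The questionnaire in Protocol Appendix 9 is redacted, so the documents do not show whether the instrument's own guidance treats components differently. The trigger is narrow: exactly one blank in ten, on one of three questions, on a form completed with a parent's or caregiver's help. Components are not protocol endpoints, and no p-value depends on them.

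Most of this stands, and it limits the point to a minor one. It does not make 0 a sound value for a component with no answer.

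A reader might also infer several stronger claims that the documents do not support.

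- *The SAP contradicts itself on one versus two blanks.* It does not. 5.1.3.1 is a threshold rule, and different inputs give different results. The threshold suits the total but works inconsistently for one-question components.
- *The tables will show false complete resolution.* That happens only when the true answer was not 0, and nothing shows how often a question is left blank.
- *The quality-of-life hypothesis is compromised.* It is tested on the change in CDLQI total (Protocol 9.1; SAP 5.3), not on components.
- *Every component should be missing if any of its questions is blank.* The argument here covers only components with a single question. The other three retain answered items.

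**Conclusion.** The point holds as a minor scoring defect. When question 7 (neither part), 9 or 10 is the only blank, SAP 5.1.3.1 records the best possible score for a component about which the form says nothing.

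The consequence is confined to descriptive summaries of component change. The limit of 3 points per form follows directly from the scoring rules. The Week 16 limits of 0.075 and 0.12 per form rest on the planned group sizes and on the least favourable true answer of 3. How many forms are affected is unknown, so no material distortion of any reported result has been shown. The place of CDLQI change in the fixed testing sequence is not in question.

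**What to change.** Keep the score-0 rule for the CDLQI total. Add one sentence to SAP 5.1.3.1:

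*The School/holidays, Sleep or Treatment component score is set to missing if its only question (Q7: neither part; Q9; Q10) is unanswered, whatever the number of unanswered questions.*

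In SAP 5.1.2.4, qualify the line that scores an unanswered question 0 so that it refers to the rules in 5.1.3.1. Otherwise it would conflict with the new sentence, and it already takes no account of the existing rule for two or more blanks.

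The cost is these two text edits and a small change to the scoring program. Descriptive component tables will hold slightly fewer values. An affected form will have a total but only five component scores, so the six can no longer be added up to the total; a table footnote should say so. The total, the CDLQI 0/1 endpoint and the tested change from baseline are unchanged.
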